**Funding Sources:**

Breast Cancer Research Foundation (BCRF)

**Study Drug:**

Ribociclib

**Clinical Phase:**

Phase IV

**Number of Patients:**

36

The study will be conducted according to the protocol and in compliance with Good Clinical Practice (GCP), with the Declaration of Helsinki, and with other applicable regulatory requirements including but not limited to Institutional Review Board/Ethics Committee (IRB/EC) approval.

## DOCUMENT HISTORY

Document	Version Date	Summary of Changes and Rationale
Original Protocol (Version 1.0)	October 13, 2020	Not applicable (N/A)
Original Protocol (Version 2.0)	December 7, 2020	Clarified inclusion criteria about brain metastases, permitted not required for participation in the study. Clarified details about the study schedule. Added an adverse event monitoring form. Clarified inclusion criteria about required labs at screening. Corrected minor grammatical errors.
Original Protocol (Version 3.0)	January 4, 2021	Updated investigator list – added [name], removed [name] Added NCT #
Protocol Version 3.1	June 3, 2021	
 
Updated protocol to include Medstar Franklin Square Medical Center as an additional site.
 
Added previously IRB approved clarification to inclusion criteria noting communication through an interpreter is acceptable.
 
Added clarification to inclusion criteria for CYP3A5 metabolizers “at least 3 participants” and “No more than 15”
 
Modified inclusion criteria minimum value for hemoglobin to allow for 8g/dl given that the FDA does not require a dose adjustment for this level. Dose adjustments are still in place for GRADE 3 events (hemoglobin < 8 g/dL) or higher, which occurred in <4% of patients in all trials referenced in the FDA label.
 
Added clarification to exclusion criteria about concurrently using other anti-cancer therapy “besides those in the study protocol”; testing for hepatitis B, hepatitis C, and HIV is not required for enrollment but if results are available then the exclusion criteria may be assessed.
 
Added clarification to the definition of uncontrolled HIV
 
Added clarification on SAE reporting.
 
Table 14.4 and 14.5 added note “*List applies to formulations of medications that are absorbed systemically”
 

Protocol Version 3.2	October 11, 2021	
 
Modified language to allow gonadotropin releasing hormone agonist as a class. Previously a specific agent, goserelin, was listed. NCCN guidelines list goserelin and leuprolide as the only available agents in the US for ovarian suppression.
 
Added clarification on enrollment procedures in the event the Georgetown Project manager is not available to confirm eligibility.
 
Added additional site Tufts Medical Center
 
Modified the PI for MWHC and the Georgetown Network
 

Protocol Version 3.3	November 10, 2021	
 
Clarified inclusion criteria to indicate lab values for Sodium, Potassium, Calcium, or Magnesium must have values within normal limits or are not clinically significant per the Investigator.
 
Clarified exclusion criteria by merging 2 related exclusion criteria into one criteria to state: Patient is concurrently using other anti-cancer therapy besides those in the study protocol (e.g., letrozole, fulvestrant, goserelin, leuprolide). Any other prior neo-/adjuvant anti-cancer therapy must be stopped at least 5 half-lives or 7 days, whichever is longer, before the date of ribociclib initiation.
 
Clarified exclusion criteria for concurrent malignancy to state: Patients may still enroll with a concurrent malignancy after receiving approval from the study PI.
 
Removed “with a systolic blood pressure >160” from Uncontrolled hypertension definition in the exclusion criteria
 

Protocol Version 3.4	January 6, 2022	
 
Updated Co-Principal Investigator for Georgetown to [name]
 
Removed [name] and Added [name] to Medstar Franklin Square Hospital
 
Section 4.3.7 clarification added “If sample size requirements (sections 3.3 and 9.1; at least 3 participants in AA or Black cohort who are CYP3A5 poor metabolizers; at least 3 participants in the NHW cohort who are CYP3A5 intermediate or normal metabolizers) are met, then CYP3A5
 

		
phenotype screening may be bypassed per Principal Investigator discretion.”
 
 
• Table 14 footnote clarification added “CYP3A5 Screening may be bypassed per Principal Investigator discretion if the necessary number of participants with each phenotype are enrolled (cohort of AA or Black participants - at least 3 poor metabolizers; cohort of NHW participants - at least 3 intermediate or normal metabolizers). If CYP3A5 is already performed it does not need to be repeated within the window of < 28 days.”
 
• Clarified Inclusion criteria that consent must be obtain prior to any screening procedures that are not standard of care.
 
• Removed upper limit of mean resting heart rate (90 bpm) from Inclusion criteria. The eligibility criterion of a heart rate between 50-90 bpm was derived from the early MONALEESA studies as that is what they used. The recent COMPLEMENT-1 trial has removed the upper limit on the heart rate in their eligibility criteria and only screen for bradycardia (< 50 bpm). Tachycardia is not listed in the FDA label as an adverse reaction, a warning, or a precaution.
 
• Clarified the grammar in section 5.6.2.
 

Protocol Version 3.5	January 30, 2023	
 
• Clarified that leukopenia is not a secondary endpoint and that the last few endpoints (i.e., 2.4.4 through 2.47) are exploratory endpoint. Not secondary endpoints. See sections 2.4 and 2.5.
 

Protocol Version 3.6	September 28, 2023	
 
• Clarifying title of Table 12 by adding “that are deemed related and clinically significant by the treating physician” to the title
 

## Glossary of Abbreviations and Terms

Table 1. Abbreviations and Terms

AA	African American
AE	Adverse event
AI	Aromatase inhibitors
ALT	Alanine transaminase
ANC	Absolute neutrophil count
AST	Aspartate transaminase
AUC	Area under the curve
CABG	Coronary artery bypass graft
CBC	Complete blood count
CDK	Cyclin-dependent kinases
CMP	Comprehensive metabolic panel
CRF	Case report form
CYP450	Cytochrome P450
DLT	Dose-limiting toxicity
ECOG	European Cooperative Oncology Group
eGFR	Estimated glomerular filtration rate
EKG	Electrocardiogram
ER	Estrogen receptor
ET	Endocrine therapy
FDA	Food and Drug Administration
GCSF	Granulocyte Colony-Stimulating Factor
GI	Gastrointestinal
HER2	Human epidermal growth factor receptor 2
HR	Hormone receptor
ICF	Informed consent form
LVEF	Left Ventricular Ejection Fraction
MI	Myocardial infarction
NHW	Non-Hispanic White
NIH	National Institutes of Health
ORR	Overall response rate
OS	Overall survival
PFS	Progression-free survival
PGx	Pharmacogenomics
PK	Pharmacokinetics
PR	Partial response

AA	African American
PR	Progesterone receptor
PS	Performance status
Rb	Retinoblastoma
SBP	Systolic blood pressure
SD	Stable disease
SERD	Selective estrogen receptor
TdP	Torsades de Pointe
ULN	Upper limit of normal

## Study Synopsis

Table 2. Study Synopsis

Title	evaLuation of variations pharmacokinEtics and phArmacogeNOmics of Ribociclib in rAce-based Cohorts: The LEANORA study
Short Title	Effect Racial Disparities in the Metabolism of Ribociclib
Protocol Number	STUDY00003100
Clinicaltrials.gov number:	NCT04657679
Phase	Phase IV
Agents	Ribociclib Fulvestrant Letrozole Goserelin or Leuprolide
Indication	Advanced HR+/HER2- breast cancer
Study Overview	
Ribociclib is an inhibitor of the cyclin-dependent kinases 4 and 6 (CDK4/6) and is approved in combination with endocrine therapy for patients with advanced hormone receptor (HR) positive metastatic breast cancer (mBC). CYP3A inhibitors increase ribociclib area-under-the-curve (AUC) by 3.2-fold; this is of clinical concern given possible associations between exposure and toxicity (e.g., QTc prolongation and neutropenia). Although there is an FDA recommendation to modify therapy for patients prescribed CYP3A inhibitors, it is unknown if modifications are needed in patients who intrinsically lack enzyme activity (e.g., genetic CYP3A5 poor metabolizers).
 
CYP3A function is largely derived from CYP3A4 and CYP3A5 isozymes in adults. It is difficult to differentiate relative contributions of CYP3A4 and CYP3A5 on CYP3A function due to sequence homology (~ 84%) and overlapping substrate specificity. Genetic variations in CYP3A5 can translate into poor, intermediate, or normal CYP3A5 metabolism of different substrates. The association between CYP3A5 genotype and drug concentrations has previously informed therapy for other drugs. Dosing recommendations based on CYP3A5 genotype tacrolimus are published by the Clinical Pharmacogenetics Implementation Consortium (CPIC). It is unknown if a similar relationship could be present for CYP3A5 and ribociclib. We hypothesize that patients prescribed ribociclib with CYP3A5 poor metabolism experience increased exposure to ribociclib and likely more toxicities.
 
Race is likely to be a significant factor when exploring ribociclib pharmacokinetics and the role of CYP3A. There are known race-based differences in CYP3A4 and CYP3A5, with CYP3A4 dominant in Non-Hispanic Whites and CYP3A5 dominant in African American/Blacks. Ribociclib pharmacokinetics have not been adequately studied in African

	Americans/Blacks as only 3% of participants in the pivotal trials ribociclib were African American/Blacks. We aim to determine the pharmacological and biochemical association between ribociclib exposure and CYP3A variants in African American/Blacks and Non-Hispanic White patients. Our findings should allow clinicians to tailor treatments to maintain therapeutic doses while limiting toxicities.
Study Duration	24-36 months
Study Center(s)	MedStar Georgetown University Hospital, Lombardi Comprehensive Cancer Center, Washington, DC MedStar Washington Hospital Center, Washington, DC MedStar, Franklin Square Medical Center, Baltimore, MD Tufts Medical Center, Boston, MA
Objectives	
Primary
 
To compare the pharmacokinetics of ribociclib at steady-state between CYP3A5 poor metabolizers and CYP3A5 intermediate or normal metabolizers in each independent race-based cohort of women with advance breast cancer.
 
Secondary
 
 
Evaluate toxicity profiles (e.g., QTc prolongation, leukopenia) between each race-based cohort
 
Characterize ribociclib pharmacokinetics in African American/Black and the Non-Hispanic White patient cohorts.
 
Conduct an exploratory candidate gene analysis of other genes with a biologically plausible role in ribociclib pharmacokinetics or therapeutic response
 

Number of Patients	36 patients
Diagnosis and Main Inclusion and Exclusion Criteria	
Key Inclusion Criteria
 
 
Histologically or cytologically proven diagnosis of HR+/HER2- breast cancer with evidence of metastatic or locally advanced disease, not amenable to curative treatment by surgery or radiotherapy
 
Women age <math>\geq</math> 18 years
 
Self identify as Black, African American, or non-Hispanic White
 
Signed informed consent form
 
Adequate hepatic, hematologic, and renal function as defined below in the body of the protocol
 
Normal baseline QTc (<450 ms)
 
Asymptomatic and treated brain metastases are permitted
 
 
Key Exclusion Criteria
 
 
Patient on active treatment with CDK4/6 inhibitors
 
Any other prior neo-/adjuvant anti-cancer therapy must be stopped at least 5 half-lives or 7 days, whichever is longer, before the date of ribociclib initiation.
 
Patient is concurrently using other anti-cancer therapy (including systemic therapy or radiation)
 

	
4) Patient has impairment of gastrointestinal (GI) function or GI disease that may significantly alter the absorption of the study drug
 
5) Patient has clinically significant, uncontrolled heart disease and/or cardiac repolarization abnormality, as defined below in the body of the protocol
 
6) Patient is currently receiving any of the following substances and cannot be discontinued 7 days prior to Cycle 1 Day 1: strong inducers or inhibitors of CYP3A4/5 -including herbal medications-, chronic dosing of corticosteroids and medications that prolong the QTc interval
 
7) Patient with symptomatic visceral disease or any disease burden that makes the patient ineligible for endocrine therapy per the investigator's judgment.
 
8) Patient has received extended-field radiotherapy <math>\leq</math> 4 weeks or limited field radiotherapy <math>\leq</math> 2 weeks prior to ribociclib initiation and has not recovered to grade 1 or better from related side effects of such therapy (with the exception of alopecia or other toxicities not considered a safety risk for the patient at investigator's discretion).
 
9) Patients with central nervous system (CNS) involvement unless they meet specific stability criteria
 
10) Liver or allogeneic bone marrow transplant

Study Design	
This prospective, multicenter, cohort study will assess ribociclib (600 mg PO daily) pharmacokinetics and pharmacogenomics in female patients with HR+/HER2- metastatic breast cancer. This design will be used for two independent, race-based cohorts: 18 African American/Black patients and 18 Non-Hispanic White patients. Women are eligible if they are older than 18, have HR+/HER2- mBC and are candidates for treatment with a CDK 4/6 inhibitor and endocrine therapy. Patients are ineligible if currently prescribed a medication that inhibits or induces the CYP3A isoenzymes, have baseline electrocardiogram abnormalities, or are otherwise considered to be ineligible for ribociclib. Participants will provide serial blood samples during the first cycle. Plasma samples will be analyzed via mass spectrometry to characterize the pharmacokinetics (e.g., <math>AUC_{0-24}</math>, <math>C_{max}</math>). Pharmacogenetic testing will be performed using the PharmacogenoScan™ microarray, which tests 4,627 markers in 1,191 genes, including variants in CYP3A4 and CYP3A5.
 
The primary outcome is powered to detect a minimum clinically meaningful change, a 2-fold change in <math>AUC</math>, which is less than the 3.2-fold change seen in the mentioned CYP3A drug interaction pharmacokinetic study. Based on CYP3A5 allelic frequencies, a sample size of 36 will provide 80% power to independently test the primary outcome in the two race-based cohorts.

Multi-Institutional Trial Management	
Personnel
 
At each site, personnel dedicated to this protocol will be:
 
 
- A study PI
 
- A research coordinator
 
- A data manager
 

	
Patient Enrollment  If a patient is being screened for enrollment, the local research coordinator must send an email within 24 hours containing the patient's name to the local Principal Investigator (PI), and to the multicenter project managers. If a patient is successfully screened, the local research coordinator must send all supporting documentation to the Principal Investigator and multicenter project managers. Patients should not start therapy until the Principal Investigator, or the local PI and the multicenter project managers have reviewed the patient's records and confirmed that the patient is indeed eligible for enrollment.
 
Data Collection and Management  Patient data will be entered into the on-line accessible database. This database is housed at Lombardi-Georgetown but is accessible anywhere there is internet access. The data manager and research coordinator at each site will attend an on-line training session so that they may learn how to enroll data into the database. All screening data should be entered prior to starting therapy, and all ongoing patient data should be entered within 10 business days of each patient visit.
 
Conference Calls  The Chairs of the study along with investigators when available and research staff will review the accrual, toxicities, and other protocol issues at weekly protocol meetings and on monthly network disease group teleconferences.

Duration of therapy	
Study will evaluate patients during the first cycle of ribociclib and endocrine therapy and on day 28 prior to the second cycle of treatment to evaluate toxicities. The protocol portion of the study will be done at this point and drug treatment will be continued as determined by the treating physician per standard of care.

Statistical Design, Feasibility, and Trial Duration	
This study will be performed at MWHC and LCCC as a part of our combined Breast Cancer Research Group. This group has a joint IRB and extensive experience collaborating in clinical trials. Each institution sees 300-400 new patients diagnosed with breast cancer each year. MWHC serves a large number of minority and underserved patient groups, including 62% African American/Black patients. A previous study in patients with breast cancer (INSPIRE) conducted at MedStar Washington Hospital Center (MWHC) enrolled 75% of all patients approached (1). Thus, 48 patients would need to be screened to enroll 36 patients. Over the past 12 months, 47 patients were treated with CDK4/6 inhibitors in these institutions.
 
The funding for this work has already been obtained. [name] award from the Breast Cancer Research Foundation will be used for this study. The National Cancer Institute) has agreed to provide for pharmacogenetic testing, pharmacokinetic analyses, perform the Pharmacogenomic microarray and provide some statistical support.

	Lastly, commercially available ribociclib in combination with endocrine therapy is standard of care and will be prescribed by participants' primary oncologist.
--	---

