- Patient has any other concurrent severe and/or uncontrolled medical condition that would in the investigator's judgment, cause unacceptable safety risks to the patient, contraindicate patient participation in the clinical study, or compromise compliance with the protocol.
- Patient has clinically significant, uncontrolled heart disease or who are at significant risk of developing QT prolongation, including any of the following:
  - Documented myocardial infarction (MI), angina pectoris, coronary artery intervention, or pericarditis within 6 months prior to study entry
  - Documented cardiomyopathy, congestive heart failure, valvular heart disease, congenital heart disease, or prior cardiac surgery
  - Left Ventricular Ejection Fraction (LVEF) < 50% (testing is not mandatory)
  - Personal diagnosis of long QT syndrome, cardiac channelopathies, family history of idiopathic sudden death, congenital long QT syndrome or channelopathies
  - Personal risk factors for Torsades de Pointe (TdP) including uncorrected hypokalemia, hypomagnesemia, or need for concomitant medications with a known risk to prolong the QT interval and/or known to cause TdP that cannot be discontinued or replaced by safe alternative medication (e.g. within 5 half-lives or 7 days prior to starting study drug, whichever is longer)
  - Clinically significant cardiac arrhythmias or conduction abnormalities, including, but not limited to ventricular tachycardia, atrial tachyarrhythmia, left bundle branch block, right bundle branch block, QRS prolongation (greater than 120 ms), intraventricular conduction delay, high-grade AV block (e.g. bifascicular block, Mobitz type II and third-degree AV block)
  - Uncontrolled hypertension
  - Inability to determine the QTc interval
- Patient is currently receiving any of the following substances and cannot be discontinued 7 days prior to Cycle 1 Day 1:
  - Concomitant medications, herbal supplements, and/or fruits that are strong inducers or inhibitors of CYP3A4/5 (section 5.6).
  - Medications that have a narrow therapeutic window and are predominantly metabolized through CYP3A4/5 (section 5.6).
  - Chronic dosing of corticosteroids such as dexamethasone and prednisone is known to lead to induction of CYP3A enzymes, thereby potentially reducing ribociclib drug exposure to sub-therapeutic levels. Systemic corticosteroid treatment should not be given during the study treatment with ribociclib, except for:

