## 4.2 Study Regimen

This prospective, multicenter, cohort study will assess ribociclib pharmacokinetics and pharmacogenomics in female patients with HR+/HER2- metastatic breast cancer. Potential trial patients will be pre-identified at participating centers.

Patients who have adequate hematologic, hepatic, and renal function will be screened for enrollment. Patients who ultimately meet the inclusion and exclusion criteria as detailed in Section 3, and desire participation, will be enrolled.

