### **5.6.3 Medications Not Recommended**

In [appendix 14.5](#) there is a list of the medications are not recommended during study treatment and within 14 days prior to the first dose of study medication and for the duration of study treatment. These medications should be excluded if possible. If they must be given, then it will be based on the investigator's judgment.

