## 9.2 Statistical Analysis Plan

Primary analyses will be performed as follows. Within each race-based cohort, the ribociclib exposure which measured by ribociclib AUC will be summarized by median [Interquartile range, IQR], and two-sample t-test if normality holds or Wilcoxon-Mann-Whitney test will be used to compare AUC between CYP3A5 poor metabolizers and CYP3A5 intermediate or normal metabolizer in each independent race-based cohort. Secondary analyses will be performed as follows. Descriptive statistics will be used to characterize the data profile, frequency and percentages for categorical variables, and mean (SD) or median [IQR] for continuous variables based on the data normalization. Multiple regression will be used to identify variables associated with ribociclib AUC. To best account for any factor that may affect ribociclib exposure, covariates to be assessed include CYP3A5 metabolism status, renal function, liver function, age, race, weight, sex, among others. Any covariates with  $P < 0.2$  on univariate analysis will enter the stepwise multiple linear regression model, with  $P < 0.05$  considered statistically significant. This methodology will also be used to assess a change in absolute neutrophil count and QTc as the outcome variable. Depending on data distribution, a two-sample t-test or Wilcoxon-Mann-Whitney test will be used for 1) a change (baseline and C1D8-C1D16) in continuous variables (e.g., QTc, absolute neutrophil count) between CYP3A5 poor metabolizers and CYP3A5 intermediate or normal metabolizers, 2) to check the association between a continuous variables and categorical risk factors. Pearson correlation coefficient or Spearman correlation coefficient will be calculated to measure the association between two continuous variables. Fisher's exact test will be used for checking the association between two categorical variables. AEs will be assessed with descriptive statistics and univariate logistic regression will assess the occurrence of specific AEs with pharmacokinetic properties (e.g., AUC,  $C_{max}$ ). The approach from the linear regressions will be adapted to logistic regression to identify covariates associated with the occurrence of grade III or IV neutropenia.

Descriptive analysis of the PRO-CTCAE adverse event log to determine frequency of adverse events by race and by CYP3A5 genotype.

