## 14.5 Medications not Recommended

Medications Not Recommended\*

Category	Drug name
Moderate CYP3A4/5 inhibitors	Amprenavir, atazanavir, casopitant, cimetidine, darunavir, diltiazem, fosamprenavir, lomitapide, netupitant, tofisopam, verapamil
Moderate CYP3A4/5 inducers	Bosentan, efavirenz, etravirine, genistein, iversivirine, modafinil, naftcillin, talviraline
Sensitive CYP3A4/5 substrates	Alpha-dihydroergocryptine, almorexant, alpaviroc, apixaban (doses < 2.5 mg only), atazanavir, atorvastatin, avanafil, bosutinib, brecanavir, brotizolam, budesonide, buspirone, capravirine, casopitant, darifenacin, darunavir, ebastine, eletriptan, eplerenone, felodipine, fluticasone, ivacaftor, lomitapide, lumefantrine, lurasidone, maraviroc, midazolam, perospirone, quetiapine, ridaforolimus, sildenafil, ticagrelor, tilidine, tolvaptan, triazolam, vardenafil, vicriviroc, voclosporin
Strong BSEP inhibitors	Bosentan, fusidate, glibenclamide, , sulindac, troglitazone (TGZ-sulfate)
MATE1 and OCT2 substrates	Acyclovir, amantadine, amiloride, cephalexin, cephadrine, cimetidine, famotidine, fexofenadine, memantine, metformin (also a substrate for OCT1, MATE1, and MATE2K), pindolol, procainamide, ranitidine, varenicline
BCRP substrates	Rosuvastatin and sulfasalazine
Medications that carry a possible risk for QT prolongation	Alfuzosin, apomorphine, aripiprazole, atazanavir, atomoxetine, bedaquiline, clozapine, dexmedetomidine, dolasetron, eribulin, famotidine, felbamate, fingolimod, foscarnet, gatifloxacin, gemifloxacin, granisetron, iloperidone, isradipine, lithium, mirabegron, mirtazapine, moexipril, norfloxacin, ofloxacin, olanzapine, ondansetron (p.o. only at 4 mg or 8 mg), oxytocin, paliperidone, pasireotide, pipamperone, promethazine, quetiapine, ranolazine, rilpivirine, risperidone, roxithromycin, sertindole, telavancin, tetrabenazine, tizanidine, tolterodine, vardenafil, ziprasidone

\*List applies to formulations of medications that are absorbed systemically

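### Does a broad synopsis sentence on CYP3A drugs, with no stated rule for patients taking a moderate one at PK sampling, undermine the primary AUC comparison?

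*Combined protocol and SAP*

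**What the plan says.** **Eligibility.** The Study Design row of the synopsis states: "Patients are ineligible if currently prescribed a medication that inhibits or induces the CYP3A isoenzymes". It gives no strength qualifier and no wash-out. Key exclusion 6 in the same synopsis is narrower. It covers "strong inducers or inhibitors of CYP3A4/5 -including herbal medications", together with chronic corticosteroids and QTc-prolonging drugs, when they cannot be stopped 7 days before Cycle 1 Day 1. Section 3.4 matches that list: "Concomitant medications, herbal supplements, and/or fruits that are strong inducers or inhibitors of CYP3A4/5". It also bars chronic corticosteroids, expressly because they induce CYP3A. Section 4.2 enrols patients who "meet the inclusion and exclusion criteria as detailed in Section 3".

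**During treatment.** Appendix 14.5 puts moderate CYP3A4/5 inhibitors ("Amprenavir, atazanavir, casopitant, cimetidine, darunavir, diltiazem, fosamprenavir" and others) and moderate inducers on the not-recommended list. Section 5.6.3 applies that list from 14 days before the first dose to the end of study treatment: "These medications should be excluded if possible. If they must be given, then it will be based on" the investigator's judgment. Section 5.6 tells patients to consult the study team before taking anything new, and records all concomitant medication at each visit.

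**Analysis.** Within each race-based cohort, section 9.2 plans a "two-sample t-test if normality holds or Wilcoxon-Mann-Whitney test will be used to compare AUC between CYP3A5 poor metabolizers" and intermediate or normal metabolizers. A secondary regression is meant to account for any factor affecting exposure: "covariates to be assessed include CYP3A5 metabolism status, renal function, liver function, age, race, weight, sex, among others". CYP3A co-medication is not named there, nor in the non-evaluable rule of section 4.3.13.

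**The concern.** CYP3A activity is the exposure this trial studies, and the eligibility texts disagree about drugs that alter it. A patient on diltiazem is ineligible under the Study Design sentence but can be enrolled under section 3.4. She could still be taking it at PK sampling.

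Section 1.2.2 gives one figure for a moderate inhibitor, a 1.9-fold rise in ribociclib AUC with erythromycin. That is close to the 2-fold difference the trial is sized to detect. The smaller phenotype group may hold only 3 patients per cohort (section 3.3), so a single exposed patient could visibly move that group's mean. Section 9.2 names no flag, exclusion or sensitivity analysis that would show this. At stake would be the estimated AUC ratio between phenotypes, and whether the synopsis describes the population actually enrolled.

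**Working it through.** **1. The eligibility texts side by side.** Of the three statements of who is excluded, two (key exclusion 6 and section 3.4) agree. The third is one sentence in a summary row that abbreviates elsewhere too: it reduces the ECG criteria to a phrase and gives the age limit as older than 18, where section 3.3 has 18 or over. Section 4.2 makes Section 3 operative.

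**2. Inputs.** From the plan: 2-fold target (1.0 on log2), SD 0.75 on log2, alpha 0.05 (section 9.1); 3 versus 15 (section 3.3); 1.9-fold AUC with erythromycin (section 1.2.2). Assumed:
- Two-sided pooled t-test on log2 AUC.
- Drug use independent of phenotype, in 5-20% of patients. The documents give no usage rate.
- A fold effect of 1.3 to 1.9. Appendix 14.4 prohibits erythromycin itself for QT risk, and the drugs in 14.5 have no figure, so 1.9 is a stand-in. The documents give no figure for moderate inducers, which would act in the opposite direction.

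**3. Reference power.** SE = 0.75 × √(1/3 + 1/15) = 0.474. Power with 16 df is 50.8%, or 55.9% by the normal approximation. The stated 80% is not reproduced at 3 versus 15 with SD 0.75. That is a separate matter; 51% serves here only as the baseline.

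**4. Use spread at random.** With a proportion q exposed, each log2 AUC gains variance q(1−q)(log2 1.9)², where log2 1.9 = 0.926. At q = 0.20 the SE is √[(0.5625 + 0.16 × 0.857) × 0.4] = 0.529. Simulation (400,000 trials per case, both layouts):

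| Use | SE (log2) | Type I error | Power, 2-fold | Power, exposed removed |
|---|---|---|---|---|
| 0% | 0.474 | 5.0% | 51% | n/a |
| 5% | 0.491 | 5.0% | 48% | 48-49% |
| 10% | 0.505 | 5.0-5.1% | 46% | 46% |
| 20% | 0.529 | 5.0% | 42-43% | 40-41% |

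The mean ratio stays at 1.00 under no difference and 2.00 under a 2-fold difference.

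**5. One exposed patient.** In a group of 3, the group mean shifts by log2(f)/3:
- f = 1.3: 0.126, or 1.09-fold.
- f = 1.9: 0.309, or 1.24-fold. A true 2-fold ratio reads 2/1.24 = 1.61 if she is one of 3 White expressors, or 2 × 1.24 = 2.48 if she is one of 3 Black poor metabolizers.

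In a group of 15, f = 1.9 gives 0.926/15 = 0.062, or 1.04-fold.

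A single user falls in the group of 3 with probability 3/18 = 17%. Averaged over where she falls, type I error is (3/18) × 8.5% + (15/18) × 4.4% = 5.1%, in line with the simulated 5.0%. Simulated power is 47-48%.

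**6. Against the precision of the primary result.** The 95% half-width is 2.120 × 0.474 = 1.006 log2, a factor of about 2.0 each way. The 0.309 shift is 0.309/0.474 = 0.65 of a standard error.

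**7. What excluding her would buy.** At 2 versus 15, SE = 0.75 × √(1/2 + 1/15) = 0.565. The half-width is 2.131 × 0.565 = 1.203 log2, a factor of about 2.3, and power is 38%. An interval that wide can hardly tell 1.61 from 2.0.

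**The case for a change.** The strongest case looks at the cohort actually realised and not at the long-run average. At 5-20% use, the chance of at least one user in a group of 3 is 1 − 0.95³ = 14% to 1 − 0.80³ = 49% per cohort. Given one user there with a 1.9-fold effect, power drops to 26% if she is a White expressor. If she is a Black poor metabolizer and there is no true difference, the false-positive rate is 8.5%. The protocol rules out tamoxifen, anastrozole and exemestane because they might disturb the PK through CYP3A, yet names no handling for moderate inhibitors. A check chosen after the AUCs are known can look selective, and prespecifying one would cost only wording.

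The arithmetic stands, and so does the omission. The weight is less than it appears. The conditional figures require use at the PK visit, placement in the small group and an effect borrowed from a prohibited drug. At 1.3-fold they soften to 41% power and 5.6% false positives. The upper end of 5-20% fits poorly with section 5.6.3, which admits these drugs only when unavoidable. The regression in 9.2 is open-ended, and section 11.3 allows concomitant medications to go to the NCI to assist the PK analysis, so the plan is not blind to them. A prespecified exclusion analysis would be least informative in the very case that motivates it.

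**Conclusion.** No change to the analysis is called for. The synopsis sentence is a clerical slip in a summary row. It conflicts with key exclusion 6, section 3.4, section 5.6.3 and Appendix 14.5, and these passages must be reconciled, with the rule left to the sponsor. Enrolment meanwhile runs on Section 3.

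The silence of 9.2 is missing detail, and filling it in advance brings no gain. On the assumptions above, the primary comparison stays unbiased with type I error of 5.0-5.1%, and loses about 3 to 9 percentage points of power at 5-20% use. A sensitivity analysis without exposed patients recovers none of that. One exposed patient among 3 moves the ratio 1.09- to 1.24-fold, well inside an interval of about a factor of 2.0 each way. Because the medication record already exists, analysts can list any exposed patient and her AUC beside the primary result as ordinary reporting.

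The conclusion rests mainly on use being unrelated to phenotype within a cohort. That is plausible: the comparison is made within race, and genotype results are neither returned to patients nor placed in the health record (sections 4.3.7 and 12.4.1). It would weaken if prescribing tracked phenotype, or if the drugs in Appendix 14.5 acted much more strongly than 1.9-fold.
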